9.2 Emergency Unblinding

In the case of a medical emergency or in the event of a serious medical condition, when knowledge of the investigational product is essential for the clinical management or welfare of the participant, an investigator or other physician managing the participant may decide to unblind that participant's treatment code.

The physician managing the medical emergency or serious condition should attempt to contact the principal investigator to discuss options prior to unblinding, and the principal investigator should approve the unblinding, when applicable. However, ensuring patient safety is the primary objective when the decision to unblind the treatment assignment is made.

The principal investigator or designated study personnel will request to unblind the participant's treatment arm. The principal investigator or treating clinician will contact St. Jude Pharmaceutical Services Department to receive the unblinding information.

All occurrences of emergency unblinding will be reported to the IRB according to the criteria established in protocol section 9.0, the DSMB, and the FDA, when applicable. In a majority of cases, emergency unblinding will occur while managing a serious adverse event (SAE), and will therefore be reported with the SAE. If the unblinding event is not directly associated with an SAE, the same timeline and mechanism for reporting SAEs will be used to notify the IRB of the event (section 9.1).

9.3 Reporting to the Sponsor and/or Federal Agencies

9.3.1. Notification of Federal Agencies by Investigator

Any unanticipated fatal or unanticipated life-threatening event judged by the PI to be at least possibly due to the study treatment, will be reported to the DSMB by e-mail and the FDA by telephone or fax as soon as possible but no later than seven calendar days after notification of the event and followed by a written safety report as complete as possible within eight additional calendar days (i.e., full report 15 calendar days total after notification of event).

Unanticipated, non-fatal and non-life-threatening adverse events that occur in on-study patients and that are considered due to or possibly due to the investigational agent, will be reported to the FDA by written safety report as soon as possible but no later than 15 calendar days of the notification of the occurrence of the event. Expected SAEs, even unexpected fatal SAEs, considered by the PI to be not related to the study, will be

reported to the FDA in the Annual Review Report along with non-serious AEs. All FDA correspondence and reporting will be conducted through the St. Jude Office of Regulatory Affairs.

Copies of all correspondence to the St. Jude IRB, including SAE reports, are provided to the St. Jude Regulatory Affairs office by the St. Jude study team. FDA-related correspondence and reporting will be conducted through the Regulatory Affairs office.

9.3.2 Recording Adverse Events and Serious Adverse Events

Adverse events and serious adverse events will be recorded using the Common Terminology Criteria for Adverse Events (CTCAE) version 5.0.

9.4 Data and Safety Monitoring Board

This study has been referred to the St. Jude Data and Safety Monitoring Board (DSMB) for regular monitoring and has been sent to the DSMB. The DSMB is charged with advising the Director and other senior leaders of St. Jude Children's Research Hospital (SJCRH) on the safety of clinical protocols being conducted by SJCRH investigators and on their continuing scientific validity. The DSMB will monitor this protocol every six months for safety events/ toxicity. Refer to the DSMB Charge and Criteria for Protocol Referral for more information regarding DSMB review.

10. DATA COLLECTION, STUDY MONITORING, AND CONFIDENTIALITY

10.1 Data Collection

Electronic case-report forms (e-CRFs) will be completed by the St. Jude Clinical Research Associates (CRAs). Data from the participant's medical record will be entered directly into a secure Trial Master database developed and maintained by St. Jude Clinical Research Informatics.

Data collection will be performed by the CRA working in the Department of Surgery. Protocol-specific data and adverse events will be recorded by the CRA in the Trial Master database. All questions will be directed to the attending physician and/or PI and will be reviewed at regularly scheduled working meetings. Adverse event/toxicity data to be collected and entered into the Trial Master database include: Time point; AE category; Grade; Onset date; Is AE permanent (yes or no); Resolved date; Relationship; Action; Outcome; Was AE serious as defined by the protocol (yes or no); AE expected (yes or

no); AE result in off treatment (yes or no); Was this an unanticipated problem (yes or no); Comments.

Regular summaries of toxicity and protocol events will be generated for the PI and the Department of Biostatistics to review. Participants will be followed for up to 6 months post-op.

10.2 Study Monitoring

This study is considered high risk (HR-3) for monitoring purposes. Protocol and regulatory compliance, including essential regulatory documentation, will be assessed as well as the accuracy and completeness of all data points relating to the primary and secondary objectives semi-annually. If the study design has strata, accrual will be tracked continuously. The first two enrollees will be monitored and 15 % of the study enrollees thereafter, semi-annually.

The PI and study team are responsible for protocol and regulatory compliance, and for data accuracy and completeness. The study team will meet at appropriate intervals to review case histories or quality summaries on participants and retain copies of the minutes which are signed by the PI.

Clinical Trials Operations (CTO) will verify informed consent documentation and eligibility status on 100% of St. Jude participants within 5 working days of enrollment completion.

Overall study conduct, compliance with primary and secondary objectives, age of majority consenting, safety assessments and reporting, and the timeliness and accuracy of database entries are monitored routinely.

Study documents routinely monitored on selected participants include medical records, database entries, study worksheets, and case report forms. Study documents are monitored for participant status, demographics, staging, subgroup assignment, treatments, investigational drug accountability, evaluations, responses, participant protocol status, off-study and off-therapy criteria, and for all other specifics as detailed in a separate study-specific monitoring plan. The study-specific monitoring plan may be revised over time, to adapt monitoring frequency and/ or intensity to a changing environment when appropriate (for example: new safety signals; positive history of compliance; all participants are in long term follow-up; or the enrollment period has ended).

The recording and reporting of Adverse Events, Serious Adverse Events (SAEs), and Unanticipated Problems (UPs) to include type, grade, attribution, duration, timeliness and

appropriateness will be reviewed by the Monitor/ CRM. The CRM will generate a formal report which is shared with the Principal Investigator (PI), study team and the Internal Monitoring Committee (IMC).

Continuing reviews by the Institutional Review Board (IRB) and Clinical Trials-Scientific Review Committee (CT-SRC) will occur at least annually. In addition, unanticipated problems are reviewed in a timely manner by the IRB.

10.3 Confidentiality

Subjects' information will be kept in secure files on secure, password protected computers. Only investigators and study staff will have access to PHI. PHI will not be shared with anyone outside SJCRH. When the data are published, no identifiers will be used that can possibly link the reported information to a given subject.

The medical records of study participants may be reviewed by the St. Jude IRB, FDA, clinical research monitors, etc.

11. STATISTICAL CONSIDERATIONS

11.1 Sample Size Consideration and Randomization

This study will be conducted as a randomized, placebo-controlled double-blind trial of the administration of TXA vs. placebo prior to a limb salvage procedure. The primary objective will be to evaluate if TXA will reduce the proportional blood transfusion volume and EBL. The sample size is calculated based on the hypothesis that the TXA administration will reduce the average total volume of red blood cell transfused per kilogram of body weight by 40% relative to the average total volume of red blood cells transfused of the placebo group. Our historical data should be representative of our proposed placebo group, and historically, the average total red blood cell volume transfused per kilogram of body weight is $19.78 \text{ mL/kg} \pm 11.38$. The distribution of the intra-or post-operatively transfused blood volume is normally distributed after $\log(1+x)$ transformation (mean=2.906, sd = 0.507). We use the two-sample t-test with unequal variances to access the primary objective through the $\log(1+x)$ transformation of proportional blood transfusion volume.

We calculate the sample size with the two-sided two-sample t-test with unequal variances for the $\log(1+x)$ transformation proportional blood transfusion volume. Nineteen patients in each group are sufficient to detect a 40% decrease of $\log(1+x)$ transformation of proportional blood transfusion volume (mean=2.435, sd = 0.488) with 0.8 power and type I error 0.05. It can be safely assumed that the number of patients who

do not require blood transfusion is less than 5%. Given the sample size, we do not anticipate the blood transfusion volume will have substantial ties at 0.

Randomization will be performed in the SJCRH Pharmaceutical Services Department by a pharmacist using the randomization program developed by the Department of Biostatistics.²⁶ The drug is clear and will be given IV. The people who would determine the transfusion volume are blinded to the treatment. The randomization is stratified by the variable pre-operative weight that leads to two strata: pre-operative weight > 45.2 kg and pre-operative weight <=45.2 kg, where 45.2 kg is the median of pre-operative weight in the historical control data underwent limb-sparing tumor resections of the proximal tibia or distal femur. The assignment ratio of the TXA group to the placebo group is 1:1.

The patients who receive only one dose due to anaphylaxis (grade 3 or 4) or seizure will be removed from the evaluation of all objectives. The anticipated rate of each toxicity is about 1%. However, the descriptive statistics will be calculated for these patients who receive only one dose, e.g., adverse events and endpoints in all the objectives. The expected accrual number for our study will be 39 patients (to yield 38 evaluable subjects).

Unacceptable toxicities consist of acute kidney injury (defined by doubling of creatinine) or anaphylaxis (grade 3 or 4) or thrombotic event or seizure. The anticipated rate of each toxicity is about 1%. Thrombotic events occurring six weeks beyond the time of surgery will not be considered related to TXA administration. A heuristic approach is used to monitor each of the three toxicities in the TXA group. For each toxicity, starting from the 3rd patient, if the number of patients with any toxicity is equal to or larger than 3, the study accrual will be paused and amendments to the protocol will be discussed with the IRB. This monitoring rule yields the largest type-I error rate 0.044 when the 20th (one patient is removed due to not receiving the 2nd dose) patient show the toxicity (the 20th patient and any two previous patients in the TXA group).

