3.2. Exclusion Criteria

- 3.2.1. Participants whose limb salvage procedure may require significant manipulation of major blood vessels.
- 3.2.2. Participants with known bone marrow deficiency resulting in red blood cell deficiency (e.g. Diamond-Blackfan anemia)
- 3.2.3. Participants receiving erythropoietin-stimulating agents (e.g. epoetin alfa)
- 3.2.4. Participants with active hemorrhagic cystitis (e.g. alkylator-induced) with gross hematuria or >50 RBCs per high powered field on urinalysis
- 3.2.5. Participants actively receiving all-trans retinoic acid (ATRA) or isotretinoin (Accutane)
- 3.2.6. Participants with known allergies to antifibrinolytics
- 3.2.7. Participants with known hypercoagulopathies
- 3.2.8. Personal history of a thrombosis or active thrombus
- 3.2.9. Participants currently on anticoagulation medications (e.g. warfarin, enoxaparin)
- 3.2.10. Participants with a history of seizures. Patients with a history of febrile seizure are eligible.
- 3.2.11. Persisting toxicity related to other systemic therapies (e.g. chemotherapy) which constitutes an unacceptable safety risk based on the judgment of the PI and/or the primary treating physician
- 3.2.12. Female participants who are currently pregnant or actively breastfeeding.
- 3.2.13. Female participants who are currently receiving estrogen-based contraception therapy.
- 3.2.14. Inability or unwillingness of research participant or legal guardian/representative to give written informed consent.
- 3.2.15. Participants enrolled in another clinical trial utilizing an IND/IDE experimental therapy.
- 3.2.16. Participants with a history of CNS disease.
- 3.2.17. Participants with known bleeding disorder.
- 3.2.18. Participants with known platelet dysfunction.

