4.1.3 Second Dose

If no unacceptable toxicities occur, a second dose of tranexamic acid/placebo (TXAKIDS) 10 mg/kg (max 1 g) IV push over 5 to 15 minutes will be given 6 hours (with a window of +/- 30 minutes) after the first dose (either intra- or post-operatively).

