4.2. Dose Modifications

4.2.1. Check BUN/serum creatinine on post-op day 3.

4.2.2. If the patient has a seizure after the first dose and prior to the second dose, the second dose will not be given.

4.2.3. An anaphylactic reaction will be considered if the patient experiences any of the following 2 symptoms during infusion: nausea/vomiting; hives, pruritis or angioedema; dyspnea, wheezing or hypoxemia; syncope; or incontinence. A sudden decrease in systolic blood pressure by >30% based on age will also be considered evidence of anaphylaxis.

4.2.3.1. In case of anaphylactic reaction, immediately discontinue infusion of study agent.

4.2.3.2. Administer diphenhydramine 1 mg/kg IV (max dose 50 mg) and epinephrine 1 mg/ml (1:1000) 0.01 mg/kg IM, max dose 0.5 mg.

4.2.3.3. Additional supportive care including oxygen, bronchodilators, steroid and vasopressor support may be administered as appropriate.

4.2.3.4. The anesthesia provider will monitor continuously for signs of allergic reaction. These signs may include bronchospasm (increased airway pressures, difficulty with ventilation), and/or skin rash. Hypotension and tachycardia can be seen when an allergic reaction progresses to anaphylactic shock and may be suspected for hypotension unresponsive to fluid bolus. If an allergic reaction is suspected, a serum tryptase level will be drawn, while

treatment for allergic reaction (i.e., Epinephrine, anti-histamines) is commenced.

4.2.3.5. Medication Hypersensitivity and Anaphylaxis Treatment Guidelines can be found at:

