5. DRUG INFORMATION

5.1 Tranexamic Acid (Cykloapron®)

Source and Pharmacology: Tranexamic acid is antifibrinolytic, antihemophilic and hemostatic agent that forms a reversible complex that displaces plasminogen from fibrin resulting in inhibition of fibrinolysis. It also inhibits the proteolytic activity of plasmin. By reducing plasmin activity, tranexamic acid also reduces activation of complement and consumption of C1 esterase inhibitor (C1-INH), thereby decreasing inflammation associated with hereditary angioedema.

Formulation and Stability: Tranexamic acid is available as an intravenous solution at a concentration of 1000mg/10mL (10mL vial). Room temperature storage is recommended (25°C or 77°F, with temperature excursions permitted from 15°C to 30°C (59°F to 86°F)).

Supplier: Commercially available from Pfizer as Cykloapron® or generic manufacturers.

Toxicity: Adverse reactions associated with the injection of Tranexamic acid include (frequency not defined): hypotension with rapid IV injection (>1 mL per minute), dizziness, allergic dermatitis, menstrual disease (unusual menstrual discomfort), diarrhea, nausea, vomiting, and blurred vision. Adverse reactions seen with all formulations that were observed to be rare (< 1%), through post marketing, and/or case reports include: allergic skin reaction, anaphylactic shock, anaphylactoid reaction, cerebral thrombosis, deep vein thrombosis, diarrhea, dizziness, nausea, pulmonary embolism, renal cortical necrosis, retinal artery occlusion, retinal vein occlusion, seizure, ureteral obstruction, visual disturbances (including impaired color vision and vision loss), and vomiting.

Dosage and route of administration including infusion times: The first dose will be given at initiation of surgical preparation, and the second dose will be given 6 hours after the first dose (either intra- or post-operatively). Dose will be given by intravenous push over 5 to 15 minutes at 10mg/kg with a maximum dose of 1 g. Dose will not be injected more rapidly than 1 mL per minute to prevent hypotension.

Dose rounding at St. Jude will be allowed according to institutional policy (See St. Jude Institutional Policy 20.03.004).

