11.2 Primary Objective

- 11.2.1. To evaluate the difference in intra-or post-operatively transfused blood volume (mL/kg) for patients undergoing limb salvage procedures who are randomized to receive perioperative tranexamic acid (TXA) versus placebo.

The intra-or post-operative volumes of transfused blood for both the TXA treated group and placebo group will be estimated with a two-sided 95% confidence interval. The blood volumes transfused per kilogram of body weight of the two groups (TXA vs. Placebo) will be evaluated using a two-sided student's t-test after $\log(1+x)$ transformation.

- 11.2.2. Accrual and study duration

This study will be conducted solely at St. Jude Children's Research Hospital (SJCRH). According to the historical data, during January of 2014 through December of 2017 (48 months), 39 patients underwent limb-sparing tumor resections of the proximal tibia or distal femur that met the inclusion criteria for our proposed study. These preliminary data suggest that the randomized controlled trial with 39 patients (TXA vs. Placebo) would be feasible in a 48 months period of time.

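### Patients who miss dose 2 because of grade 3–4 anaphylaxis or seizure are dropped from every objective, and no as-randomised analysis is stated; the expected effect is small and the change costs little

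*Combined protocol and SAP*

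**What the plan says.** Section 11.1 states that patients who "receive only one dose due to anaphylaxis (grade 3 or 4) or seizure will be removed from the evaluation of all objectives". It then adds that "the descriptive statistics will be calculated for these patients who receive only one dose, e.g., adverse events and endpoints in all the objectives". Accrual of 39 to yield 38 evaluable patients allows for this loss, and each event is expected at about 1%.

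The primary objective in section 11.2 is about patients "who are randomized to receive perioperative tranexamic acid (TXA) versus placebo". Sections 11.1 to 11.4 define no other analysis set and no sensitivity analysis that keeps the removed patients.

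Section 5.1 names "anaphylactic shock, anaphylactoid reaction, cerebral thrombosis, deep vein thrombosis, diarrhea, dizziness, nausea, pulmonary embolism, renal cortical necrosis, retinal artery occlusion, retinal vein occlusion, seizure" among the effects introduced by "Adverse reactions seen with all formulations that were observed to be rare (< 1%), through post marketing, and/or case reports include". Both reasons for removal are therefore recognised drug reactions.

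On the second dose, section 4.1.3 says it "will be given 6 hours (with a window of +/- 30 minutes) after the first dose" if there is no unacceptable toxicity. Section 4.2.2 adds: "If the patient has a seizure after the first dose and prior to the second dose, the second dose will not be given". Appendix IV makes dose 2 conditional on creatinine not having doubled, and section 8.2.2 covers a second dose missed for any unacceptable toxicity. The removal rule names only anaphylaxis and seizure.

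Seizure appears both as an off-study criterion (8.1.7) and as an off-therapy criterion (8.2.1.3). Anaphylaxis is listed by name only as off-therapy (8.2.1.2).

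**The concern.** An event that occurs after the first dose, and that the drug may cause, decides who enters the comparison. If such events are more common on TXA, patients leave the two arms unequally and the remaining groups are no longer those that randomisation produced. Blinding does not prevent this, because a drug effect acts whether or not anyone knows the assignment. Arms of 19 or 20 are small enough that one patient is about 5% of an arm.

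The rule also follows no single principle. A patient who misses dose 2 after doubled creatinine is not named for removal and so, on the wording, stays in; one who misses it after a seizure goes out.

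There is a data question as well. Section 11.1 promises endpoints for the one-dose patients, but a seizure takes the patient off study. If study data collection then stops, neither the promised description nor a later as-randomised analysis may be possible.

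**Working it through.** **Inputs.** From section 11.1, on the log(1+x) scale: placebo mean 2.906, SD 0.507; TXA mean 2.435, SD 0.488; difference 0.471; two-sided 0.05; 19 per group; 39 accrued; about 1% for each event. The historical mean of 19.78 mL/kg is in sections 2.2 and 11.1. Assumptions made here: 20 TXA and 19 placebo patients when all 39 are kept; a low value of 5 mL/kg; and, as a lower-rate scenario, half of the events falling before dose 2.

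**The plan's own figures.** Noncentral-t power for the unequal-variance test is 0.788 at 18/18 and 0.810 at 19/19, so 19 per group reproduces. With 2% removed, 38 / 0.98 = 38.8, which rounds up to 39 and also reproduces.

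**How many are removed.** Taking 1% + 1% = 2%:
- Expected number: 39 × 0.02 = 0.78.
- At least one: 1 − 0.98^39 = 0.545. Two or more: 0.183.
- If events occur only on TXA (20 patients), at least one: 1 − 0.98^20 = 0.332.

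These are upper values unless the 1% is read as the rate before dose 2, because only events in the roughly six hours between doses lead to removal. The exclusion criteria also keep out "Participants with known allergies to antifibrinolytics" and patients with a history of non-febrile seizures. At half the rate (assumption): 0.39 expected; 1 − 0.99^39 = 0.324; TXA only, 1 − 0.99^20 = 0.182.

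**What one removal does.** With the other 19 TXA patients at the planned mean, keeping rather than removing a patient with volume x changes the TXA mean by (ln(1+x) − 2.435)/20.

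| Removed patient | ln(1+x) | Change in TXA mean if kept | Share of 0.471 | Removal favours |
|---|---|---|---|---|
| At the placebo log mean | 2.906 | +0.024 | 5.0% | TXA |
| 19.78 mL/kg | 3.034 | +0.030 | 6.4% | TXA |
| 5 mL/kg (assumption) | 1.792 | −0.032 | 6.8% | placebo |

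The 19.78 mL/kg value is the raw historical mean. It lies above the placebo mean on the analysis scale, so the 5.0% row is the one for a placebo-like patient.

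**Effect on the test.** In 300,000 simulated trials (19 placebo, 19 TXA, plus one TXA patient fixed at x), power is 0.81 with that patient removed. Kept, it is 0.77 at 19.78 mL/kg and 0.86 at 5 mL/kg. For a patient typical of the TXA arm, power at 19 placebo and 20 TXA is 0.82. At 19.78 mL/kg, 4.1% of trials are significant only because the patient was removed. Weighted by the TXA-only chance of a removal, this is 0.332 × 0.041 = 1.4% of trials, or 0.182 × 0.041 = 0.7% at half the rate.

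**Risk in keeping the patient.** Dose 1 is given at initiation of surgical preparation (4.1.1), so a reaction could precede incision. The documents do not mention postponement; it is assumed here. If surgery were postponed and the volume scored as 0, the TXA mean would change by (0 − 2.435)/20 = −0.122, which is 25.8% of 0.471 in favour of TXA. About 6.5% of simulated trials would be significant only because of that zero. This is larger than the effect of removal, so an as-randomised set needs a rule for this case.

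**The case against.** The rule is prespecified and worded alike for both arms, the trial is double-blind, accrual allows for one loss, and the removed patients' endpoints are to be described. With usually no patient or one involved, a reader could largely see what had been left out. If the removed patient simply resembles the rest of the TXA arm, removal creates significance in 1.2% of simulated trials and loses it in 2.2%. All of this stands and keeps the severity low. It does not supply the missing comparison, since a description of the removed patients is not a between-group analysis that includes them.

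Three stronger readings are tempting.
- A reader might infer that the planned set is a two-dose set, or only patients who tolerated dose 1, particularly as the toxicity-monitoring text in section 11.1 speaks of a patient removed for not receiving the second dose. The removal sentence does not support this: it names two causes, and one-dose patients with doubled creatinine are not among them. The plan is closer to as-randomised than that reading implies.
- A reader might infer that removal flatters TXA. The table shows that the direction depends on the removed patient's volume.
- A reader might infer that all removed patients go off study. By name, the conflict concerns seizure only. Appendix III also classes most evaluations as standard of care, so transfused volumes should normally be in the medical record. The open question is whether study collection continues.

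**Conclusion.** The point holds at low severity. The plan lets a possibly treatment-caused event after randomisation decide who is compared, applies this to some one-dose patients and not others, and states no as-randomised analysis. At the stated rates fewer than one removal is expected, and one removal on TXA moves that arm's mean by about 5% to 7% of the planned difference over the values tried, in either direction. These sizes rest on the plan's 1% per event, on 20 TXA patients, and on the assumed volumes. They would grow if the events were several times more frequent or the removed patients more extreme. The documents do not support saying that the result would be materially biased or that the trial is underpowered.

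**What to change.** 1. Make all randomised patients, analysed in their assigned arm, the main set for the between-group comparisons: 1.1.1 first, then 1.2.1 to 1.2.3, 1.3.1 and 1.3.3. Keep the set defined in section 11.1 as a sensitivity analysis. The association analyses (1.2.4, 1.3.2) need not change.
2. State a rule for surgery postponed after a reaction to dose 1. Do not score the volume as 0. Use the volume transfused for the limb salvage operation when it takes place, in the assigned arm; if no operation takes place, treat the outcome as missing. Fix the same rule for both arms before unblinding.
3. Reconcile 8.1.7, 8.2.1.3 and the promise in section 11.1 of endpoints for one-dose patients, so that study data collection continues for them.

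The cost is wording, and accrual stays at 39. The downside is that the estimate then includes patients without the full regimen. Power moves slightly: 0.82 if the retained patient is typical of the arm and 0.77 if a retained TXA patient had 19.78 mL/kg, against 0.81 with removal.

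### The accrual-pausing rule in 11.1 lists four toxicities, monitors three, says both each and any, and states an error rate that fits only the four pooled

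*Combined protocol and SAP*

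**What the plan says.** Four sentences in section 11.1 define the rule.

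- The list has four items: "Unacceptable toxicities consist of acute kidney injury (defined by doubling of creatinine) or anaphylaxis (grade 3 or 4) or thrombotic event or seizure". Each is put at about 1%.
- An attribution window for one of the four follows: "Thrombotic events occurring six weeks beyond the time of surgery will not be considered related to TXA administration".
- The monitoring sentence has three items: "A heuristic approach is used to monitor each of the three toxicities in the TXA group". It does not name them.
- The trigger reads "For each toxicity, starting from the 3rd patient, if the number of patients with any toxicity is equal to or larger than 3", at which point accrual is paused and protocol amendments are discussed with the IRB.

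The operating characteristic comes next: "This monitoring rule yields the largest type-I error rate 0.044 when the 20th" TXA patient shows the toxicity.

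Two other places bear on the point. Section 8.2.1, the off-therapy criteria, lists three unacceptable toxicities: acute kidney injury, anaphylaxis and seizure, without thrombotic event. Section 9.4 provides for periodic review: "The DSMB will monitor this protocol every six months for safety events/ toxicity".

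**The concern.** A pausing rule has to say which events count and whether they are counted together. This one leaves both open. The number of toxicities changes from four to three between neighbouring sentences. The trigger starts toxicity by toxicity and then counts patients with any toxicity. The 0.044 cannot belong to all of these readings.

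The readings lead to different decisions. Suppose two TXA patients have a thrombosis within six weeks and a third has a kidney injury:

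- four toxicities pooled: three patients counted, so accrual pauses;
- each toxicity counted separately: the largest count is two, so there is no pause;
- the three toxicities of section 8.2.1, however counted: only the kidney injury counts, so there is no pause.

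Whether thrombosis counts matters here. Section 4.4.1 itself warns that clot risk may be raised in the TXA group, because these patients have cancer and may have central lines. If staff apply the rule per toxicity, the IRB has a much less sensitive safeguard than the 0.044 suggests.

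**Working it through.** **Inputs** (section 11.1): boundary of 3 patients, applied from the 3rd TXA patient on; 1% per toxicity; n = 20 TXA patients, consistent with 39 accrued at 1:1.

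**Formula.** The boundary stays at 3, so the chance of ever reaching it by patient 20 equals the chance of 3 or more events among 20:

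P(X ≥ 3) = 1 − (1−p)^20 − 20p(1−p)^19 − 190p²(1−p)^18

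**The plan's own figure.** With four toxicities pooled and the rates added, p = 4 × 0.01 = 0.04:

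1 − 0.4420 − 0.3683 − 0.1458 = 0.0439, which rounds to the stated 0.044.

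**Other readings at n = 20:**

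| Reading | p | Type I error |
|---|---|---|
| Four pooled, rates added | 0.04 | 0.0439 |
| Four pooled, independent (1 − 0.99^4) | 0.0394 | 0.0423 |
| Three pooled, rates added | 0.03 | 0.0210 |
| Three pooled, independent (1 − 0.99^3) | 0.0297 | 0.0205 |
| One toxicity alone | 0.01 | 0.0010 |
| Three separate rules, at least one crossed: 1 − (1 − 0.0010)^3 | 0.01 each | 0.0030 |
| Four separate rules, at least one crossed: 1 − (1 − 0.0010)^4 | 0.01 each | 0.0040 |

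A different sample size does not rescue another reading. Four pooled gives 0.0384 at n = 19 and 0.0497 at n = 21. One toxicity at 1% gives 0.0070 even at n = 39. Solving for the rate that yields 0.044 at n = 20 returns 4.0%.

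The ratio of four pooled to one toxicity alone, from unrounded tails, is 43.7.

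**Chance of a pause by patient 20 if true rates are higher** (all rates here are assumptions; the plan gives none beyond 1%):

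| Assumed rates | Four pooled | Separate rules |
|---|---|---|
| All four at 2% | p = 0.08: 0.21 | 1 − (1 − 0.00707)^4 = 0.03 |
| All four at 3% | p = 0.12: 0.44 | 1 − (1 − 0.02101)^4 = 0.08 |
| Thrombosis 10%, others 1% | p = 0.13: 0.49 | thrombosis rule alone: 0.32 |

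**The case against.** The best case for leaving this alone is that it is loose wording around a correct number. The plan calls the rule heuristic. Crossing it pauses accrual and does not end the trial. The DSMB meets every six months, and the study team reviews grade 3 to 5 events throughout. No efficacy analysis, sample size or analysis set is touched. The 0.044, the word *any* and the thrombosis window placed just before the rule all point to four pooled, so the intent can be inferred. All of this stands and limits the consequence. It does not settle the rule: staff should not have to work back from a binomial tail to learn what to count, and the documents give the DSMB no numerical threshold of its own.

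A second objection is that the text may really mean a per-toxicity rule. *Each of the three*, the opening of the trigger sentence and the singular *the toxicity* in the closing sentence all favour that. This is fair, and it is why the fix covers both readings. But on that reading the 0.044 is wrong by a factor of about 44.

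Third, section 8.2.1 may be where *three* comes from. That list serves a different purpose, which is taking a patient off study drug. If it is the source, the doubt about whether thrombosis counts becomes stronger.

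Finally, the 44-fold ratio compares false-alarm rates, not harm, and raising all four rates together flatters pooling. If only thrombosis is raised, to an assumed 10%, the advantage falls to about 1.5-fold (0.49 against 0.32). The gap narrows but remains.

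**Conclusion.** The concern holds. The rule as worded and its stated error rate do not describe the same procedure. Among the readings the text allows, 0.044 at 20 TXA patients arises only when all four toxicities are pooled at a combined 4%. Three pooled gives 0.021, and a single-toxicity rule gives 0.001 (0.003 across three such rules, 0.004 across four). The fault lies in the wording; the 0.044 is sound for the pooled rule. These figures rest on the plan's 1% per toxicity, a fixed boundary of 3 and independent patients. The exact match to 0.044 also needs the four rates simply added, since treating the toxicities as independent gives 0.042. Because this is the plan's only numerical accrual-pausing rule and the readings can disagree on the same data, it should be corrected. The harm is bounded by the nature of the rule and by DSMB review.

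**What to change.** The sponsor should state which rule is meant.

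If pooled, which the 0.044 supports, change the monitoring sentence in 11.1 to refer to the four toxicities combined, delete the opening *For each toxicity*, and state the rule along these lines:

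> Starting from the 3rd TXA patient, accrual is paused when 3 or more TXA patients have had any of the four toxicities (type I error 0.044 at 20 patients, combined rate 4%).

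The six-week thrombosis sentence stays as it is.

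If per toxicity, remove *any*, name the toxicities monitored, say whether thrombosis is among them, and restate the error as about 0.001 per toxicity (0.004 across four, 0.003 across three).

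Either way, naming the events in 11.1 prevents the shorter off-therapy list in 8.2.1 from being taken for the pausing list. The cost is two sentences of wording, with no new data and no change to sample size or analysis set.
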